### 12.3.3. Informed consent procedures of first and second-degree relatives

Study results on genetic variants of SOD1, C9orf72, FUS and TARDBP genes might be of diagnostic and therapeutic relevance of study participant's first and second-degree relatives. Relatives may include individuals with symptoms of ALS or FTD (established or probable diagnosis of fALS) as well as asymptomatic individuals (unknown risk of ALS). In principle, study participants are offered to provide the genetic study results to authorized family members. However, the knowledge and awareness about genetic research of study participants might be perceived as psychologically burdensome for first and second-degree relatives. The information includes the advice of genetic counseling prior to the notification of genetic study results. The study information and the offered genetic counselling will address the potential medical, psychological and social burden that can be associated with pathogenic gene mutations as well as the individual or societal benefits aimed with the study. Therefore, the provision of the study participant's genetic study results will be restricted and must comply with the following requirements:

- Authority for provision of study results to first and second-degree relatives by the study participant in a written manner
- Written information to first or second-degree relatives on the option of receiving genetic results of study participant
- Genetic counseling of first or second-degree relatives prior to signing informed consent on receiving genetic results of study participant
- Informed consent of first or second-degree relatives for receiving the study participant's genetic study results
- Directives of first or second-degree relative about the notification criteria of study participant's genetic results

The relative's directives concerning the notification criteria is part of the informed consent procedure. The notification criteria for relatives are the same as for the patient (see Table 12). The study results might be provided to authorized first and second-degree relatives after the death of the study participant (postmortem provision of participant's genetic study results).

*Table 12: Differentiated provision of genetic study results to first and second-degree relatives and modes of notification*

Patient's directive	Notification	Provision of study results
no notification	not applicable	not applicable
notification about all individual study results	by request of relative	provision of study results to genetic consultant for subsequent use in genetic counseling

notification about selected study results with therapeutic relevance	by study center	Counseling by study neurologist and referral to genetic consultant
--	-----------------	--

#### **12.3.4. Genetic consultation of first and second-degree relatives**

First and second-degree relatives of study participants will be advised for genetic counseling 1) prior to signing the informed consent on receiving genetic results of study participant and 2) prior to notification of study participant's genetic results (when the relative has signed the informed consent). The subject of the counseling will be differentiated according to the patient's directives and the genetic study results. An overview on the scheme of genetic counseling is provided in Table 12. As part of the study, recruiting study sites are prepared to refer patients (or their advice seeking relatives) to certified geneticists who are experienced in the consultation on genetic variants in ALS. The genetic results of the study participant will be provided by the study on request of the genetic consultant and used for counseling of first and second-degree relatives. In case that study results are of therapeutic relevance, first and second-degree relatives will be actively informed by study center and invited respectively to genetic counseling by the study neurologist. Subsequently, a referral to a certified geneticist will be offered. For referral, the relative will receive study results being handed over to the certified geneticist. The genetic counseling of the first and second-degree relatives is considered independent from this observational study and is not subject of this study protocol.

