Sample size determination:	Due to this partly exploratory background of study project, a sample size justification is not applicable. The sample size is based on the feasibility of eligible patients to be enrolled at this site and is not based on power calculation.
Interim analysis:	An interim analysis may be performed.
Study stopping rules:	Not applicable for an observational study.

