## **3. Objectives and endpoints**

### **3.1. Objectives**

#### **3.2. Primary objective**

- To identify the frequency of genetic variants in the genes of SOD1, C9orf72, FUS and TARDBP in patients with sALS and fALS

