## **5. Study subjects**

### **5.1. Number of study subjects**

2,000 subjects are planned to be recruited. More than 1000 subjects are expected to complete the end-of-study assessments, after an observation period of 12 months.

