### **6. Enrollment of subjects**

The enrollment of subjects takes place in specialized ALS-outpatient centers in Germany. ALS patients being eligible for the investigation, will be invited to participate in this cohort study. After obtaining informed consent, subjects will be enrolled in the study. Approximately, 2,000 subjects will be observed in this study. Participating sites will be informed once 2,000 subjects have been enrolled.

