#### 9.4. Family history

The number and degree of relatedness of family members who are living with ALS (or FTD) or who died of ALS (FTD) will be investigated. Furthermore, family members suffering from any neurological/psychiatric disorder or who died of any neurological/psychiatric disorder will be determined. A first-degree relative (FDR) is a person's parent (father or mother), full sibling (brother or sister) or child. It constitutes a category of family members that largely overlaps with the term nuclear family, but without spouses. A second-degree relative (SDR) is someone who shares 25% of a person's genes. It includes uncles, aunts, nephews, nieces, grandparents, grandchildren, half-siblings, and double cousins.

Table 5: Items used to describe the family history of ALS or FTD

Item	1 st degree relative (n)	2 nd degree relative (n)
ALS (living)	Suspected Probable Definite Genetically confirmed	Suspected Probable Definite Genetically confirmed
ALS (deceased)	Suspected Probable Definite Genetically confirmed	Suspected Probable Definite Genetically confirmed
FTD (living)	Suspected Probable Definite Genetically confirmed	Suspected Probable Definite Genetically confirmed
FTD (deceased)	Suspected Probable Definite Genetically confirmed	Suspected Probable Definite Genetically confirmed
Neurological/psychiatric disorder (living)	Definite	Definite
Neurological/psychiatric disorder (deceased)	Definite	Definite

n = number of individuals

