Patients who refuse to be notified about study results will not be informed about the outcome of genetic analysis. This patient's directive explicitly includes pathogenic mutations that might be of diagnostic or therapeutic relevance. The patient's directive of notification of all genetic study results will include normal findings (no or benign variants) genetic, genetic variants of unknown significance and pathogenetic mutations (likely pathogenic or pathogenic genetic variants in the investigated genes of SOD1, C9orf72, FUS and TARDBP. Results of diagnostic relevance are defined as genetic variants being known to cause ALS or can increase the risk of ALS or can modify the phenotype of the disease including the progression rate. The finding of pathogenic variants can lead to the diagnosis of fALS although the disorder – given the negative family history of ALS – has prior been classified as sALS. The diagnostic relevance can extend to other family members as likely pathogenic or pathogenic mutations in the study at ALS genes might substantiate a genetic risk for ALS to first- and second-degree relatives of study participants. Therapeutic relevance is defined by the planning or performance of a phase 3 clinical trial, a planned or ongoing early access program or an expected approval of genetic medicine targeting one of the studied genes within the next 12 months. Currently, therapeutic relevance can be stated for mutations found in the SOD1 gene. Therapeutic relevance of C9orf72 and FUS can be expected within the next few years post-approval of this study protocol. The definition of diagnostic and therapeutic relevance and the scheme of notification of individual study results is provided in table 11.

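### Relatives of SOD1 carriers may be contacted and could then enrol, but the plan neither links participants of one family nor allows for relatedness in the analysis

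*Combined protocol and SAP*

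**What the plan says.** **Objective.** Section 3.2: "To identify the frequency of genetic variants in the genes of SOD1, C9orf72, FUS and TARDBP in patients with sALS and fALS". The unit is the patient.

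**Contact with relatives.** Section 12.3.4 says that, for results of therapeutic relevance, "first and second-degree relatives will be actively informed by study center and invited respectively to genetic counseling by the study neurologist". Section 12.3.1 adds: "Currently, therapeutic relevance can be stated for mutations found in the SOD1 gene". It expects C9orf72 and FUS to follow within a few years, and section 12.3.5 has the definition reviewed at least every 12 months.

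**Conditions on contact.** Section 12.3.3 requires the participant's written authority, written information and counselling for the relative, the relative's own consent, and the relative's directive. Table 12 shows contact by the study center only under the directive for selected results of therapeutic relevance. Under the directive for all results, contact is at the relative's request.

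**Who the relatives are.** Section 12.3.3: "Relatives may include individuals with symptoms of ALS or FTD (established or probable diagnosis of fALS"; asymptomatic relatives are also covered.

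**Enrolment.** Section 6: "ALS patients being eligible for the investigation, will be invited to participate in this cohort study". Sections 5.2 and 5.3 do not mention relatives of participants. Under Table 11 the study neurologist obtains informed consent.

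**Data and analysis.** Section 9.4 and Table 5 collect "The number and degree of relatedness of family members who are living with ALS (or FTD", and the same for deceased relatives, but no field shows whether a relative is a participant. Section 11 lists Fisher's exact, chi-square, Mann-Whitney and t-tests, linear regression and 95% confidence intervals. It gives no per-family rule, clustering or sensitivity analysis for relatedness.

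**The concern.** Read together, these sections leave a route that currently opens for one gene only. A SOD1 finding can lead the center to contact the family and bring a relative to the study neurologist, the role that also takes consent for the study. If that relative has ALS, section 6 applies. Families with no mutation, or with a mutation in another gene, get no such contact at present.

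Two separate consequences are possible:

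- **Selection.** If contact makes related SOD1 carriers likelier to enrol than other patients, the SOD1 frequency is raised. The effect falls mainly on familial ALS (fALS), a group named in the primary objective.
- **Dependence.** Two relatives who share a mutation are not independent observations. Intervals for the frequency, and for the SOD1 versus no-mutation comparison, would be too narrow. This applies to any related pair, however they came to enrol.

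The plan records neither kinship between participants nor the route of enrolment, so the final data could not reliably show whether either had occurred.

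**Working it through.** The documents give no expected SOD1 count and no precision target (the synopsis says the sample size "is not based on power calculation"), so there is no planned figure to reproduce. The following is an illustration.

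**Inputs from the documents**
- N: "2,000 subjects are planned to be recruited" (section 5.1), held fixed at 2,000.
- SOD1 frequency: 14.8% in fALS and 1.2% in sporadic ALS (sALS) (section 2.1).
- sALS is more than 90% of patients (section 2.1), so the fALS share f is below 10%.
- C9orf72: 6.5% overall, 34% in fALS, 5% in sALS (section 2.1). Solving 0.34f + 0.05(1 − f) = 0.065 gives f = 0.015/0.29 = 5.2%.

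**Assumptions**
- k related SOD1 carriers take k of the 2,000 places. The documents give no value; 0, 2, 5 and 10 are shown.
- f is 10% or 5.2%.
- The relatives are classed as fALS, since each has an affected relative in the study.

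**Baseline, k = 0**
- f = 10%: fALS carriers 0.148 × 200 = 29.6; sALS carriers 0.012 × 1,800 = 21.6; total 51.2, or 2.56%.
- f = 5.2%: 0.148 × 104 = 15.4; 0.012 × 1,896 = 22.8; total 38.1, or 1.91%.

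**With k relatives**, let s = 1 − k/2,000:
- fALS frequency = (fALS carriers × s + k) / (fALS patients × s + k)
- overall frequency = (all carriers × s + k) / 2,000

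For k = 5, s = 0.9975:
- f = 10%: fALS (29.53 + 5)/(199.5 + 5) = 34.53/204.5 = 16.9%; overall (51.07 + 5)/2,000 = 2.80%.
- f = 5.2%: fALS (15.35 + 5)/(103.74 + 5) = 20.35/108.74 = 18.7%; overall (38.05 + 5)/2,000 = 2.15%.

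| k | fALS, f = 10% | fALS, f = 5.2% | Overall, f = 10% | Overall, f = 5.2% |
|---|---|---|---|---|
| 0 | 14.8% | 14.8% | 2.56% | 1.91% |
| 2 | 15.6% | 16.4% | 2.66% | 2.01% |
| 5 | 16.9% | 18.7% | 2.80% | 2.15% |
| 10 | 18.9% | 22.3% | 3.05% | 2.40% |

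**Scale**
- Five relatives raise the fALS figure by 14% to 26% in relative terms. To reach five, 5/29.6 = 17% (f = 10%) or 5/15.4 = 32% (f = 5.2%) of fALS SOD1 carriers would each have to bring in one affected carrier.
- Exact 95% intervals in fALS are about 10.4% to 20.7% (30/200) and 8.3% to 22.7% (15/104). All tabulated fALS values lie inside the matching interval.
- Each relative adds about 0.05 points overall. About 12 to 14 are needed to move the overall frequency by one 95% half-width (0.60 to 0.69 points).
- The sALS frequency stays at 1.2%.

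**Dependence.** With m related pairs among n carriers and complete within-family correlation, the variance factor is 1 + 2m/n. For m = 5:
- f = 10%: 1 + 10/56.1 = 1.18, a standard error about 9% larger.
- f = 5.2%: 1 + 10/43.0 = 1.23, about 11% larger.

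Lower correlation gives less.

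**The case against.** A reader might infer that the study recruits relatives of SOD1 carriers, that one family mutation is therefore counted more than once, and that the SOD1 frequency is inflated. The documents do not support that, for these reasons:

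- No section says that a contacted relative enrols. Section 12.3.4 invites relatives to counselling and declares that counselling independent of the study.
- Contact depends on written authority, consent and directives.
- Few relatives would qualify. Those who are asymptomatic or have only FTD do not meet section 5.2. What remains is a relative living with ALS at the same time, in a disease that section 2.1 describes as fatal within a few years. Some would attend a participating center and be invited anyway, and those cause no selection bias.
- The objective is a per-patient frequency. Two affected relatives are two ALS patients, so counting both is not in itself an error.
- Related subjects are not wholly untraceable. Exact variants (section 9.9), family-history counts, three-digit postcodes (Table 2) and the written authorities and consents allow a partial check.
- The gene-specific contrast may fade if therapeutic relevance extends to C9orf72 and FUS.

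All of this stands and limits the claim to a possibility of modest size. It also argues against making one subject per family the primary analysis: that changes the quantity estimated, and dropping notified relatives would remove carriers who would have enrolled anyway. It does not remove the gap. A shared variant does not prove kinship, the route of enrolment is not listed among the study data, and dependence between relatives needs no active contact.

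**Conclusion.** The concern holds as a possibility that the plan could not reliably detect, not as a demonstrated bias. The SOD1 frequency in fALS could be raised if contact makes related carriers likelier to enrol than other patients, and intervals would be somewhat too narrow if related carriers are treated as independent. The number of such relatives is unknown; at zero there is no effect.

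The fALS figures are illustrative. They rest on an assumed number of relatives, the two fALS shares and a fixed total of 2,000. The overall frequency is little affected unless about ten or more relatives enrol. For an exploratory registry with no formal hypothesis this is a cheap improvement rather than a flaw that undermines the primary result. It is best made during enrolment, because the link and the route can only partly be reconstructed later.

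**What to change.** 1. Add two eCRF fields at enrolment: (a) whether a first- or second-degree relative is already enrolled, with a pseudonymized family ID; (b) whether enrolment followed notification of a relative's study result.
2. In section 11, keep the per-patient frequency as primary. Prespecify a sensitivity analysis with one index subject per family (the first enrolled) and with subjects flagged under (b) excluded.
3. Use family-clustered standard errors for the frequency intervals and the genotype comparisons.
4. Reconcile section 12.3.4 with Table 12 on when the center contacts relatives. The section sets no limit by directive, whereas the table does.

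The cost is two fields, a few sentences in section 11 and slightly wider intervals. No relative is refused enrolment or testing. If few related subjects enrol, the two sets of results will nearly agree and the report can say so.

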#### **12.3.5. Follow-up on study results with therapeutic relevance**

Therapeutic relevance is defined by the planning or performance of a phase 3 clinical trial, a planned or ongoing early access program or an expected approval of a genetic medicine targeting one of the studied genes within the next 12 months. The principal investigator and the genetic review board will analyze, review and interpret published information on the planning, beginning and completion of phase 3 clinical trials, early access programs or approvals of genetic medicines targeting one of the studied genes. The therapeutic residence will be defined as described at least every 12 months for 3 years after the beginning of the study. The extension of this review activity is of great scientific and medical value and will be subject of further investigations and related protocols.

#### **12.4. Insurance and reimbursement**

Not applicable for an observational study.

#### **12.5. Data protection and confidentiality**

The subject will not be identified by name in any of study reports being solely used for research purpose. The ethics committees, and various government health agencies can inspect the records of this study. Every effort will be made to keep the subjects' personal medical data confidential. This register study is subject to the regulations set forth in the Data Protection Act which shall be fully adhered to. APST and the Charité agreed on the Order Data Processing (ODP) Agreement in accordance with Council of the European Union General Data Protection Regulation (EC-GDPR; transl: *EU-Datenschutzgrundverordnung, EU-DSGVO*). The patient data shall be pseudonymized for further processing and statistical analysis. For this purpose, the patient data shall be encoded. Data assessment shall take place exclusively using the encoded (pseudonymized) data sets so as to exclude any tracing of an individual patient's identity. Data pseudonymization shall be performed in accordance with the regulations set forth in the general data protection regulation (§ 4 clause 5 DSGVO). The APST shall be responsible for the storage and processing of patient data that have previously been captured via the study software (studioMED+). The patient data is stored in an encrypted and pseudonymized pattern

in a database on its own root server in Germany. In addition, a principle of roles and rights is integrated, which guarantees decryption and de-pseudonymization only for authorized persons.

## **12.6. Access rights to personal data**

Participants in the study are entitled to view any of their personal data captured in the context of the study. At that, patients themselves – or their authorized proxy - are granted the option to receive a print copy of all the data captured on clinical research software (studioMED+). Patients are furthermore entitled to notify us of any errors in the data captured on them and to request data correction.

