## **8.2. Data collection**

Data will be collected from various sources and by different means. Some data are obtainable retrospectively as from medical records (at study sites) and platform-based registry (APST platform). Other data will be collected prospectively using on-site or assessments.

Data defined in the protocol will be assessed and captured by different means:

- Data from medical records and on-site assessments: data on clinical characteristics, family history, interventions and health care measures) will be collected on data sheets and transferred to predefined data fields on the web-based study software “studioMED+” or may be captured on the electronic case report form (eCRF) of “studioMED+” directly.
- Data from remote assessment: data from digital self-assessments (ALS-FRS, MYMOP) will be captured on a smart phone application (“ALS-App”) and stored in the data base of the APST platform (<https://www.ambulanzpartner.de/>). The “ALS-App” serves as a mobile application of the APST platform.
- Data from genetic laboratory: molecular genetic analysis will be performed on blood samples provided by study participant. Results from the genetic investigation will be generated by the genetic laboratory and transferred to predefined data fields on the web-based study software “studioMED+”.
- Data on health care measures: data on the provision with assistive technology (complex power wheelchairs, communication devices, robotic assistive systems, symptomatic pharmacotherapy, physical, occupational and speech therapy will be captured on the APST platform directly.

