Given the potential, diagnostic and therapeutic relevance of individual study results on genetic variants of SOD1, C9orf72, FUS and TARDBP genes, all study participants are offered the principal option to be informed about the result of genetic investigation. Conversely, the knowledge and awareness about own study results – encompassing the potential implications for genetically related family members – might be perceived as psychologically burdensome. Therefore, study participants will be informed about the requirement to select between notification options of their individual study results. Study participants who decided to be notified about the genetic study results are offered to seek genetic consultation prior to the notification of study results. The offered genetic consultation will include the information on the mutation type, the interpretation of results (benign, likely benign, likely pathogenic, pathogenic or variant of uncertain significance) as well as the potential medical, psychological and social implications of the findings. The procedure of genetic counseling is described in more detail in section 12.3.3. Study participants will be informed that genetic study results of uncertain significance may be discussed within the genetic review board which is described in section 10.3. The patient's directive concerning the notification about the individual study results is subject to the study information and mandatory part of the informed consent. Study participants are requested to select one of the following options of notification about individual study results:

- No notification about genetic study results
- Notification about all genetic study results
- Notification about selected genetic study results with therapeutic relevance

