## **12.7. Archiving**

Data from all different primary data sources (see 8.3) shall be captured and stored on the clinical research software (studioMED+). Any data from questionnaires that have been filled in manually shall be transferred to the eCRF component of studioMED+. All the data shall be pseudonymized and transferred to suitable computer programs for statistical evaluation. Following statistical analysis, the results shall be illustrated and published as tables, graphs, and in text format. The publishing of the results shall take place in strict observation of the DSGVO, thus excluding the possibility of tracing an individual patient's identity. The pseudonymization of data excludes by guarantee any direct or indirect linking of data to personal patient information and the identification of individual patients. The pseudonymized cohort study data used for statistical and scientific purposes are not subject to any data retention or erasure period. The data captured in the context of this study shall be retained for a minimum of 10 years following study completion. Data erasure is not envisaged with the objective of upholding care research in the long term. The erasure of single data sets is exempt from this regulation and shall be performed upon the respective patient's request or upon withdrawal of the respective patient's consent to participating in the study at any time and without giving reasons.

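### Section 12.6 gives access to all study data with no exception for the notification directive, so a requested copy can disclose genetic results that 12.3.1 says the patient will not be told

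*Combined protocol and SAP*

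**What the plan says.** **Access.** Section 12.6 contains two rights. The first covers viewing: "Participants in the study are entitled to view any of their personal data captured in the context of the study". The second covers copying: patients, or an authorized proxy, "are granted the option to receive a print copy of all the data captured on clinical research software (studioMED", that is, in studioMED+. Neither is limited by type of data, neither mentions the notification directive, and proxy is not defined.

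**Where the genetic results are kept.** Section 8.2 states: "Results from the genetic investigation will be generated by the genetic laboratory and transferred to predefined data fields on the web-based study software", which it names as studioMED+. Section 12.7 repeats this for the study as a whole: "Data from all different primary data sources (see 8.3) shall be captured and stored on the clinical research software (studioMED".

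**What the patient may be told.** Section 12.3.1 makes the directive a mandatory part of consent, with three options: no results, all results, or only those with therapeutic relevance. The first option reads "No notification about genetic study results". Its effect is stated without qualification: "Patients who refuse to be notified about study results will not be informed about the outcome of genetic analysis". The next sentence adds: "This patient's directive explicitly includes pathogenic mutations that might be of diagnostic or therapeutic relevance".

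**What a relative may be told.** Section 12.3.3 restricts provision to first- and second-degree relatives and lists five requirements: the participant's written authority, written information, counselling, the relative's own informed consent, and the relative's own directive. The counselling item reads: "Genetic counseling of first or second-degree relatives prior to signing informed consent on receiving genetic results of study participant". Table 12 marks provision to relatives as not applicable where the patient chose not to be notified.

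**The concern.** The directive is the protocol's main protection against unwanted genetic knowledge. Section 5.3 excludes anyone who cannot give one. Sections 12.3.1 and 12.3.3 both recognise that such knowledge can burden patients and relatives. Table 11 pairs the no-notification choice with refusal of genetic consultation before the study, so these patients may be the least prepared for a result.

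Section 12.6 opens a second route to the same information and does not consult the directive. A patient who wants a printout of visit scores would, on the text as written, receive the genetic fields with it. Disclosure cannot be undone. What is at stake is participant protection and the promise made at consent; no estimate is at risk.

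**Working it through.** No arithmetic applies. The check is whether the sections can all be followed at once.

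**Step 1: are the genetic results within what 12.6 releases?** Yes. Section 8.2 sends the laboratory results to studioMED+, 10.1 says that data from all the different sources are captured and processed there, and 12.7 says they are stored there. The cross-reference in 12.7 points to 8.3, which is the molecular genetic analysis section. Whether or not 8.1 or 8.2 was meant, genetic data are covered. The fields concerned are those of Table 10: variant present or absent, mutation type, and classification.

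**Step 2: compare each directive with a literal 12.6 copy.**

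| Directive | May be told (12.3.1, Table 11) | A full copy contains | Conflict |
|---|---|---|---|
| No notification | Nothing, pathogenic findings included | Results for all four genes | Direct |
| Therapeutic relevance only | Likely pathogenic or pathogenic variants with a treatment option; 12.3.1 currently names SOD1 | Results for all four genes, every classification | For everything outside the selection |
| All results | Everything | Everything | None as to content |

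**Step 3: the proxy.** Section 12.6 asks only that the proxy be authorized. If the proxy is a first- or second-degree relative, a full copy hands that person the participant's genetic result. The authorization might partly meet the first of the five requirements in 12.3.3. The remaining four (information, counselling, consent, own directive) would not have been met by anything in 12.6. This step depends on who the proxy is, which the documents do not say.

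**Step 4: does any other section reconcile them?** None does.
- The roles-and-rights rule in 12.5 limits decryption and de-pseudonymization to authorized persons. It does not filter by directive, and 12.6 itself entitles the recipient.
- The sealed-envelope and de-pseudonymization procedure in 12.3.2 governs results passed on for external genetic consultation. It does not govern access requests.
- Section 12.3.1 does not say that an access request changes the directive, and no procedure for changing it is described.

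**The case against.** The strongest reply is that the two sets of rules govern different acts. Section 12.3.1 governs what the study tells a patient; 12.6 is an option that the patient must exercise. A person who asks for all their data can be said to have chosen to see it. The consent form was also not available for this review and may explain how an access request interacts with the directive.

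Part of this stands. Nothing is released without a request, so a reader should not infer that 12.6 discloses results automatically. But 12.3.1 promises without qualification that these patients will not be informed, and a request for one's study data is not stated to be a request for the genetic result. The reply supplies a rule that the protocol lacks.

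Three stronger readings are tempting and are not supported:
- **That counselling is breached for every patient.** Section 12.3.1 makes counselling before notification an offer, and 12.6 does not withdraw it. For patients who chose all results there is no conflict with the directive.
- **That relatives will receive results.** No section says that a proxy is, or usually is, a relative. The undefined term leaves this possible and no more.
- **That the number harmed can be estimated from the carrier rates in 2.1.** Those rates bear on carriers, not disclosures. The documents give no split of directives and no rate of access requests. In addition, SOD1 carriers who chose therapeutic relevance are currently due that result anyway.

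**Conclusion.** The conflict is real and confined to specific cases. For a patient who chose no notification and asks for a full copy, 12.6 and 12.3.1 cannot both be followed as written. For a patient who chose therapeutic relevance, the same holds for every result outside that selection. The possible bypass of 12.3.3 through a proxy is weaker, because it needs the proxy to be a first- or second-degree relative.

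The conclusion assumes that a site applies 12.6 literally, and that no text outside the reviewed document, such as the consent form, already limits it. The number of participants affected cannot be derived, and no count should be attached. The primary endpoint, the sample size and the analysis in section 11 are unaffected. The change is worth making because a stated rule, correctly followed, would defeat a recorded consent choice, and the repair is small.

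**What to change.** Reconcile 12.6 with 12.3.1 and 12.3.3:

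1. State that both the viewing right and the default print copy leave out the genetic fields of Table 10 unless the directive on file covers them. Changing the print copy alone would leave the viewing sentence as an equivalent route.
2. State that a participant may obtain the remaining genetic fields by expressly asking for them in writing, that this is recorded as a change of directive, and that genetic counselling is offered first. Add a line to 12.3.1 describing how a directive is changed.
3. Define the authorized proxy, and state that a proxy who is a first- or second-degree relative receives the genetic fields only once the 12.3.3 conditions are met.

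The cost is a few sentences in 12.6 and 12.3.1 and an export from studioMED+ that takes account of the directive. The downside is one extra written step for a participant who wants the genetic data. Access is not denied, which should keep the change compatible with the data-protection rules adopted in 12.5. The protocol does not set out their content, so the sponsor should confirm this before amending.
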